5.3 Study Drug Supplies

- **Formulation and Packaging**
Medication will be received directly from MEEI Pharmacy department.
Medication will come on a syringe with only patient's information on it.

- **Preparing and Dispensing**

Medication will be prepared on-site by the MEEI Pharmacy.

- **Administration**

Medication will be administered in the Ophthalmic Plastic and Reconstructive Surgery clinic on the main MEEI building. Injection will be placed on the corresponding affected area of each patient.

5.4 Study Drug/Device Storage and Accountability

- Medication will be prepared and stored by MEEI Pharmacy Department as by their protocol.
- Medication disposable or destruction upon completion as per MEEI Pharmacy Department.

5.5 Other Medications

- **Administration**

No limitation in concomitant medication use prior or during the clinical study participation.

- **Rescue Medication or Therapy**

No identifiable rescue medication or therapy that can be used during the participation in the clinical study.

7. STUDY PROCEDURES

7.1 Screening Procedures

- Every patient that comes to the clinic requiring a full thickness skin graft to reconstruct the periocular area (meets the inclusion and exclusion criteria) will be offered the opportunity to participate on the clinical trial study.

7.2 Enrollment/Baseline Procedures

- Every patient will undergo periocular reconstructive surgery with the use of a skin graft. Afterwards (2-3 weeks later) will start receiving the injections.

7.3 Study Drug or Device Procedures

- Every patient that participates on the study will obtain a physical examination with emphasis on the affected area in every visit. Plus patient will be required to fill out a scar assessment questionnaire. Also a photograph will be taken to monitor changes objectively.

7.4 Standard of Care Procedures

- No matter the patient's enrollment in the study, all patients will obtain the appropriate surgical procedure without deviation of the normal surgical routine. Follow up will be kept the same.

7.5 Follow-up Procedures

- After patient receives last injection, he will be followed 3 more times (2-3 week after last injection, and 6 and 12 month post-op from original surgery date). During those visits, patient will be required to fill out a questionnaire and will obtain a physical examination by the physician and photos will be taken.

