1.2 Rationale

- There have been two retrospective studies that have investigated the safety and efficacy of 5-FU injected in periorbital skin grafts with or without Kenalog. The first (Massry 2011) used post-operative injections of a 50:50 mixture of 5-FU and triamcinolone for correction of medial canthal webs. In 2 patients, they found it to be safe and effective. The author noted he has used it previously for other scar management cases and was “very pleased with the results and [had] negligible side-effect[s].” The same author performed another study using 5-FU for skin grafts. This study evaluated 19 patients who had skin grafts for various purposes and were injected following surgery (similar to our protocol). This study demonstrated safety of the injection, with no cases of complication. The author concluded that the 5-FU is effective with “minimal scarring, high patient and surgeon satisfaction, and few complications
- Medication will be injected in the periocular skin graft area 2-3 weeks after surgery. The medication will be injected every 2-3 weeks for a total of up to four injections. Concentration of medication is 50mg/ml. Medication will be administered using a 1cc syringe with a 30gauge needle.

- Any competent patient (male or female) from the age of 18 to 89 that presents with any periocular pathology that requires skin graft for reconstruction and consents to participate will be a candidate to be included in the study.
- To your knowledge 5-FU hasn't been withdrawn from research or market in any country for any reason related to its safety or effectiveness.

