3. STUDY DESIGN

3.1 Study Design Description

- Randomized double blinded study comparing 5-FU versus placebo.
 - Patients will be randomized between treatment and control group. Double-masked study, neither patient nor physician providing treatment will know which group they are participating. Pharmacy will provide medication (5-FU versus saline).
 - Subject will be evaluated on first visit for the periocular pathology referred to our clinic requiring a full thickness skin graft to reconstruct the affected area. On that same visit patient will be scheduled to have surgery and research study will be presented. Whether or not patients decide to participate on study, surgery will be performed as normal. Then patient will be seen one week post-op as all surgical patients are normally seen. If patients decide to participate, 1-2 weeks later will start injecting medication (5-FU versus saline) on affected area. Injections will be repeated three more times, for a total of up to four, in a period of 2-3 weeks between each injection. After last injection is placed, patient will be seen 2-3 weeks after, and then 6 and 12 months after original surgery date. During each visit after surgery patient will be required to fill a scar assessment questionnaire.

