5. STUDY DRUG(S)/DEVICE(S)

5.1 Study Drug Information

- Study drug that will be administered to fifteen of our patients is 5-Fluorouracil, FDA-approved systemic chemotherapy medication to treat certain cancers, the concentration 50 mg/ml and will inject less than 1cc total in the subcutaneous tissue of the affected area.
- Study placebo that will be administered to the other fifteen of our patients is sodium chloride 0.9% (PF).
- Medications will be given every 2 to 3 weeks for a total of 4 injections.
- The amount of medication injected will depend on the extension/dimension of the periocular area affected with a maximum dose of 1cc total.

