8. SAFETY AND EFFECTIVENESS ASSESSMENTS

8.1 Safety Assessments

- Patients will be asked in each visit after surgery for any adverse events or complain from surgery or injection. It will be documented in the record as normally done with any patient.
- The PI will be responsible for safety review. Physician may withhold any injection if there is an adverse event like infection

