9. ADVERSE EVENT RECORDING AND REPORTING

9.1 Recording Requirements

- Research subjects will be routinely questioned about treatment related adverse events at each study visit. All possible, if any, non-serious examples are pain, erythema/redness, skin thinning/atrophy, infection, color/texture change, swelling, telangiectasia, graft shrinkage/rejection and need for additional surgery. Serious adverse events are not expected to be seen at any moment of the study since medication has been shown to be safe to the patient. In addition, patients will be evaluated for early post-operative complications (within 2 weeks of surgery) not related to study drug treatment. Example of that are wound dehiscence, graft necrosis, infection, bleeding, partial/complete graft failure and/or ectropion. Events will be followed until it resolves or stabilizes; if needed other treatment (eg. antibiotics) will be added to manage adverse event.

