#### **10.6 Safety Analysis**

- The safety analysis of the study drug is our secondary endpoint that will be analyze with a sample t-test using a level of significance of 0.050.

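### Assessment visits before month 6 are timed from the injections given, so patients who stop early have fewer scheduled adverse-event enquiries, and unequal stopping can make ascertainment differ between arms

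*Protocol*

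**What the plan says.** **Visits.** Protocol 7.5: "After patient receives last injection, he will be followed 3 more times", once 2-3 weeks after that injection and then at 6 and 12 months from surgery. In the 7.8 schedule the first-injection visit is timed from surgery. The second, third and fourth injection visits, and the one that follows the fourth, are each timed from the injection before. There is no row for a patient whose injections have stopped. SAP 10.4 defines the last time point of the POSAS model in the same way, relative to the last injection.

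**Injections.** Protocol 1.2: "The medication will be injected every 2-3 weeks for a total of up to four injections". Protocol 3.1: "Injections will be repeated three more times, for a total of up to four, in a period of 2-3 weeks between each injection". Protocol 5.1 gives a fixed number: "Medications will be given every 2 to 3 weeks for a total of 4 injections". These statements need to be reconciled. Protocol 8.1 adds "Physician may withhold any injection if there is an adverse event like infection", and 7.7 says much the same.

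**Adverse-event enquiry.** Protocol 9.1: "Research subjects will be routinely questioned about treatment related adverse events at each study visit". Section 8.1 also places the enquiry at each visit after surgery.

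**After stopping.** Protocol 9.3 keeps collecting data to 12 months, without injections, from a patient withdrawn for an adverse event. It gives no visit dates and leaves that patient out of the analysis. Protocol 13.1 has data collection end at withdrawal. SAP 10.4 promises an intention-to-treat comparison of all randomised subjects, then excludes anyone partially treated. SAP 10.6 says "The safety analysis of the study drug is our secondary endpoint that will be analyze with a sample t-test" and names neither the variable nor the population.

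**The concern.** Adverse events are a secondary endpoint, and the scheduled means of finding them is the question asked at visits. If the number of visits depends on how many injections a patient received, the intensity of looking depends on something that happens after randomisation and may itself be a response to treatment. Should one arm have more stopped courses, that arm would have fewer scheduled chances to record a new or repeat event. Its POSAS assessments would also be fewer and earlier. With about 15 patients per arm, a few missed enquiries can matter. An enquiry that was never made cannot be recovered at analysis, whichever population is chosen.

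**Working it through.** **Inputs.** Three visits after the last injection (7.5). Injections 2-3 weeks apart, up to four (1.2, 3.1). First injection 2-3 weeks after surgery, and one earlier post-operative visit (7.8). Month 6 is taken as week 26.

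**The plan's own figure.** On the full course, 7.8 shows three visits after the fourth injection: 2-3 weeks later, 6 months and 12 months. This matches 7.5.

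**Visit counts for k injections.**
- After the first injection: (k - 1) + 3 = k + 2.
- All visits after surgery: 1 + k + 3 = k + 4.
- The visit after the last injection falls at weeks 2 + 2k to 3 + 3k, so the gap to week 26 runs from 26 - (3 + 3k) to 26 - (2 + 2k) weeks.

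| Injections given | Enquiries after the first injection | All visits after surgery | Post-last visit (week) | Gap to month 6 (weeks) |
|---|---|---|---|---|
| 1 | 3 of 6 (50%) | 5 of 8 (63%) | 4-6 | 20-22 |
| 2 | 4 of 6 (67%) | 6 of 8 (75%) | 6-9 | 17-20 |
| 3 | 5 of 6 (83%) | 7 of 8 (88%) | 8-12 | 14-18 |
| 4 | 6 of 6 | 8 of 8 | 10-15 | 11-16 |

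The count also holds when the patient attends for the second injection and it is withheld for good, because that attendance is then the visit 2-3 weeks after the last injection.

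**POSAS timing.** Read literally, the last time code in SAP 10.4 falls at weeks 4-6 for a patient with one injection and at weeks 10-15 for a patient with four.

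**Arm level (assumed stopping).** If 3 of 15 patients stop after one injection, mean enquiries are (3 x 3 + 12 x 6)/15 = 5.4 instead of 6, or 10% fewer. If 5 of 15 stop, the mean is (5 x 3 + 10 x 6)/15 = 5.0, or 17% fewer.

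**What this does to recorded events.** The documents give no event rates. Assume an independent probability p of a report at each visit, with p = 0.05, 0.10 and 0.20.

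1. *Every event reported at one of the three later injection visits stops the injections, and all patients are analysed.* The proportion with any event is unchanged (26.5%, 46.9%, 73.8%), since each stopped patient has already reported one. Expected visits are 3p + 4p(1 - p) + 5p(1 - p)^2 + 6(1 - p)^3 = 5.71, 5.439, 4.952. The mean number of visits with a report is p times that: 0.285, 0.544, 0.99, against 0.30, 0.60, 1.20. The falls are 5%, 9% and 17% (1 - 4.952/6 = 0.17).
2. *A different event after such a stop.* A patient stopped at the second-injection visit has 2 scheduled looks left instead of 5. At p = 0.10, detection is 1 - 0.9^2 = 19% against 1 - 0.9^5 = 41%.
3. *Stopping after one injection for reasons unrelated to events.* In those patients, the probability of any recorded event is 1 - (1 - p)^3 = 14.3%, 27.1%, 48.8%, against 1 - (1 - p)^6 = 26.5%, 46.9%, 73.8%.
4. *As case 1, but stopped patients are excluded, as SAP 10.4 says of partial treatment.* The any-event proportion falls to 14.3%, 27.1%, 48.8%. That loss comes from the exclusion and not from the visit count.

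**The case against.** A reader might infer that the arm with more stopped injections must look safer by construction. The documents do not support that. SAP 10.6 names no safety variable, and a patient stopped for an event has already reported it, so an any-event proportion need not fall (case 1). A reader might also infer that stopped patients are in general asked half as often. Half is the one-injection extreme, counted after the first injection only; over all visits after surgery it is 5 of 8.

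Further points on the other side:
- No passage cancels the remaining visits. Section 7.8 lists injection in a separate column from the assessments, and 9.3 removes injections but not data collection. Even so, 7.5 and 7.8 do time the visits from injections, and 9.3 sets no dates, covers only adverse-event withdrawals and conflicts with 13.1.
- Unscheduled visits are allowed (7.6) and reported events are followed until they resolve or stabilise (9.1). These are real safeguards, but the first depends on a patient needing to be seen and the second concerns events already known. Neither replaces systematic enquiry for new ones.
- Visits at 6 and 12 months are fixed from surgery. Lasting changes could still be seen there, a later enquiry covers the time since the previous one, and fewer injections mean less exposure. The constant-p model therefore probably overstates the loss.
- If the exclusions in 9.3 and SAP 10.4 apply to safety, these patients' data leave the comparison and extra visits would not change it. That stands, but SAP 10.4 also promises intention to treat, and withholding an injection is not withdrawal.
- The final graft measurement is unaffected for a patient who stays in follow-up, because the primary test uses only the pre-treatment and last values.

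**Conclusion.** The point holds as a limited one about ascertainment. As written, stopping after 1, 2 or 3 injections leaves 3, 4 or 5 scheduled adverse-event enquiries after the first injection instead of 6, and stopping after one lengthens the gap to month 6 from 11-16 weeks to 20-22. If stopping differs between arms, detection of new or repeat events and the timing of POSAS data can differ between arms.

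Neither a direction nor a size of bias can be stated. Both depend on the safety variable, which the SAP leaves undefined, and on stopping rates, which the documents do not give. The illustrations range from no change in an any-event proportion to a marked loss in patients stopped early for unrelated reasons. They rest on assumed per-visit probabilities and on the patients being kept in the analysis. This is a cheap improvement to ascertainment and safety monitoring, not a demonstrated bias in favour of 5-FU.

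**What to change.** In Protocol 7.5 and 7.8, state that the assessment visits (examination, adverse-event enquiry, graft measurement, questionnaire, photograph) keep the originally planned 2-3 week calendar, through the visit planned after the fourth injection slot, and then 6 and 12 months, whether or not an injection is given. Leave the injection decisions unchanged. Word the last POSAS time point in SAP 10.4 to match that calendar.

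For these data to count:
- reconcile Protocol 9.3 with 13.1 on data collection after withdrawal;
- reconcile the intention-to-treat statement in SAP 10.4 with the exclusion of partially treated or withdrawn patients in SAP 10.4 and Protocol 9.3, at least for the safety analysis;
- name the safety variable and population in SAP 10.6.

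The cost is a short wording change. A patient whose injections stop attends up to three visits without an injection, all already in the schedule, with no new procedure.

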7.6 Unscheduled Visits

- If patient needs to be seen sooner for any reason, it will be allowed and documented in the study.

7.7 Early Termination

- If early results show that medication have serious adverse reaction, not seen in any of the previous published studies, then study will be stopped and patients will be informed of the event. Study physician may withhold any injections if there is an adverse event like infection.

7.8 Schedule of Activities (Study Table)

	Intervention (injection)	Physical examination	Questionnaire	Photograph
Initial evaluation (screening)		X		X
Surgery				X
First post- operative visit		X		X
2-3 weeks after surgery (1 st injection)	X	X	X	X
2-3 weeks after 1 st injection (2 nd injection)	X	X	X	X
2-3 weeks after 2 nd injection (3 rd injection)	X	X	X	X

2-3 weeks after 3 rd injection (4 th injection)	x	x	x	x
2-3 weeks after 4 th injection		x	x	x
6 months after initial surgery		x	x	x
12 months after initial surgery		x	x	x

8. SAFETY AND EFFECTIVENESS ASSESSMENTS

8.1 Safety Assessments

- Patients will be asked in each visit after surgery for any adverse events or complain from surgery or injection. It will be documented in the record as normally done with any patient.
- The PI will be responsible for safety review. Physician may withhold any injection if there is an adverse event like infection

8.2 Effectiveness Assessments

- Effectiveness of the study medication will be evaluated by measuring skin graft in each visit after surgery. The measurements will be recorded and analyzed at the end of the study to evaluate the graft size change during the whole study and compare the two groups. Photos will be taken also to objectively observe and document changes. Scar assessment will be evaluated with the use of a questionnaire completed by the observer/surgeon and patient. Questionnaire will be stored and at the end of the study values will be analyzed.

9. ADVERSE EVENT RECORDING AND REPORTING

9.1 Recording Requirements

- Research subjects will be routinely questioned about treatment related adverse events at each study visit. All possible, if any, non-serious examples are pain, erythema/redness, skin thinning/atrophy, infection, color/texture change, swelling, telangiectasia, graft shrinkage/rejection and need for additional surgery. Serious adverse events are not expected to be seen at any moment of the study since medication has been shown to be safe to the patient. In addition, patients will be evaluated for early post-operative complications (within 2 weeks of surgery) not related to study drug treatment. Example of that are wound dehiscence, graft necrosis, infection, bleeding, partial/complete graft failure and/or ectropion. Events will be followed until it resolves or stabilizes; if needed other treatment (eg. antibiotics) will be added to manage adverse event.

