9.3 Withdrawal of Subjects due to Adverse Events

- If subject presents with a serious event from intervention, he/she will be withdrawn from further study intervention and the investigators will evaluate the reason for event. If patient states a minor adverse event patient will continue unless patient wishes to voluntary withdraw.
- A serious event includes a severe allergic reaction to medication causing systemic symptoms of anaphylaxis.
- Data will continue to be collected from the withdrawn subjects, until 12 months after original surgery date, but without further intervention (no more injections) and patient will not be included in the analysis.

Withdrawn subjects from study participation due to an adverse event will not be replaced for a new patient.

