11. DATA AND SAFETY MONITORING

11.1 Data and Safety Monitoring Plan

- Safety review will take place on site on every follow up visit by the examining physician that will monitor all patients for any complication or side effect from treatment; if serious treatment will be stopped. All adverse events and unanticipated problems will be reported to the Human Studies Committee as previously explained. Every examining physician has the expertise and knowledge to identify any complication from the treatment each patient is receiving. Each physician and member of the study has completed MEEI training. Each month, the study will be assessed by the PI and study coordinator to evaluate for significant adverse or treatment effects. All data collected will be stored in a locked cabinet inside the oculoplastics administrative office.

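### Treatment-related graft rejection and reoperation are labelled non-serious whatever their outcome, so at that label neither mandatory stop of the patient's injections applies

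*Protocol*

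**What the plan says.** Protocol 9.1 first says that patients will be asked about treatment-related events at each visit, then gives the list: "All possible, if any, non-serious examples are pain, erythema/redness, skin thinning/atrophy, infection, color/texture change, swelling, telangiectasia, graft shrinkage/rejection and need for additional surgery". It adds: "Serious adverse events are not expected to be seen at any moment of the study". Graft necrosis and graft failure appear separately, as early complications of the first two weeks after surgery that are not attributed to the study drug.

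Protocol 9.3 has two rules for injections after an adverse event. One is for serious events: "If subject presents with a serious event from intervention, he/she will be withdrawn from further study intervention". The other is for minor events: "If patient states a minor adverse event patient will continue unless patient wishes to voluntary withdraw". The only illustration of the first category is: "A serious event includes a severe allergic reaction to medication causing systemic symptoms of anaphylaxis". Patients withdrawn for an adverse event are followed to 12 months after surgery and are not replaced, "but without further intervention (no more injections) and patient will not be included in the analysis".

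Protocol 11.1 adds: "Safety review will take place on site on every follow up visit by the examining physician", whose task is to "monitor all patients for any complication or side effect from treatment; if serious treatment will be stopped". It also provides for a monthly assessment by the principal investigator and the coordinator. Protocol 7.7 and 8.1 permit, but do not require, the physician to withhold an injection, with infection as the example. Protocol 13.2 ends the whole study if the treatment proves harmful.

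**The concern.** Seriousness normally depends on what happened to the patient, not on the name of the event. Here two events that can mean loss of the graft are placed in the non-serious class in advance, and the mandatory stops depend on that class. A physician who follows the list would find no rule requiring the injections to end.

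What is at stake is continued dosing of a graft that may be failing because of the drug. Protocol 1.1 describes 5-FU as suppressing fibroblast proliferation and collagen production. It also treats repeat surgery as a morbidity and notes that some patients have little or no spare donor skin. A written rule would make the decision consistent across physicians, who are masked to the assignment.

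**Working it through.** No alpha, power or sample-size figure bears on this point. The check sets 9.1 against every provision that stops or withholds injections, then bounds the exposure from the visit schedule.

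**Which provisions apply to a treatment-related rejection or reoperation taken at its 9.1 label**

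- 9.3, serious event: mandatory stop, but the label is non-serious. Not triggered.
- 9.3, minor event: the patient continues. A rejected graft is hardly minor, so this rule does not clearly apply either. An event that is neither serious nor minor has no rule.
- 11.1: mandatory stop, again only for a serious event. Not triggered.
- 7.7 and 8.1: withholding is allowed. This is discretion, not a duty.
- 11.1, monthly review: looks at the study as a whole and sets no rule for one patient's next injection.
- 13.2: ends the study once harm is shown. It also sets no rule for one patient.

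No section gives general criteria for seriousness that would override the label.

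**Share of the list affected**

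The nine items are pain; erythema/redness; skin thinning/atrophy; infection; colour/texture change; swelling; telangiectasia; graft shrinkage/rejection; further surgery. The point concerns two: the rejection half of the eighth, and the ninth. Shrinkage is the primary endpoint and is left aside. Infection is already named in 7.7 and 8.1 as a reason to withhold.

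**Exposure window** (Protocol 3.1, 5.1, 7.8: first injection 2–3 weeks after surgery, then every 2–3 weeks, up to four)

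- Earliest fourth injection: 2 + 3 × 2 = week 8.
- Latest fourth injection: 3 + 3 × 3 = week 12.
- Injections left to discretion after an event following injection k: 4 − k, that is 3, 2, 1 and 0 for k = 1, 2, 3 and 4.

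**What a stop would do to the analysis**

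Under 9.3 a patient withdrawn for an adverse event leaves the analysis and is not replaced. SAP 10.4 names an intention-to-treat comparison but also excludes and replaces anyone partially treated. Protocol 13.1 replaces such patients and collects data only up to withdrawal, although it refers back to 9.3. A new stop rule with nothing else changed would therefore remove patients with failed grafts from the comparison of graft size.

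**The case against.** The strongest reply is that this is only a preference for a fixed rule over clinical judgement. The items in 9.1 are examples, and 9.3 says that serious events include anaphylaxis, so neither list is closed and a physician may judge a particular rejection serious. A physical examination is scheduled at every injection visit. The course is described in 3.1 as up to four injections, so a shorter one is already allowed. The principal investigator is responsible for safety review, which includes the monthly assessment. All of this stands, and it limits the practical effect. None of it supplies a mandatory stop, and the label still points the physician away from the one that exists.

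It is also fair to say that the label is not wrong in every case. Protocol 1.1 discusses repeat surgery mainly as a consequence of scarring and shrinkage, and a cosmetic revision may well be non-serious. The remedy must therefore leave such surgery out.

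Three stronger readings are tempting and are not supported:

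- *The protocol requires injections to continue into a rejected graft.* It does not. The instruction to continue covers minor events only, and withholding is always open.
- *These events would escape reporting to the Human Studies Committee.* That would need listed events to count as expected, which no section says. The committee policy named in 9.2 is not reproduced, and 9.2 also has a route for unanticipated problems.
- *The label biases the treatment comparison by a calculable amount.* Any shift in the arm means would come from the exclusion rules in 9.3 and 10.4, not from the label, and would rest on an assumed deficit in the excluded patients.

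**Conclusion.** The point holds as a gap in the patient-level stopping rule. At the 9.1 label, treatment-related graft rejection and reoperation fall outside both mandatory stops, and up to three injections are left to discretion. It affects two of nine listed items and matters only from the first injection to the fourth; after the fourth nothing remains to stop. The documents give no rate for these events, so the expected number of affected patients in a trial of up to 30 cannot be stated.

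The conclusion assumes that the physician takes the label as written. Where a case is judged serious despite the label, 9.3 and 11.1 work as intended. The change should be made because it is cheap and concerns patient safety, but the existing backstops mean that the plan is not without protection.

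**What to change.** 1. **Protocol 9.1.** Remove the blanket non-serious label and grade each event by outcome: death, threat to life, hospitalisation, lasting disability or loss of function, or surgery needed to prevent one of these.
2. **Protocol 9.3, stop rule.** State that injections end for that patient, whatever the grade, after graft rejection or loss, or after unplanned surgery on the study graft for a reason other than shrinkage or cosmetic revision, when possibly related to the injection.
3. **Protocol 9.3, analysis.** Replace the exclusion from analysis with inclusion in the intention-to-treat comparison already named in SAP 10.4. Keep the existing follow-up to 12 months and the existing rule against replacement.
4. **SAP 10.4 and Protocol 13.1.** Add one line to each so that they defer to 9.3 for these patients.
5. **Value used in the intention-to-treat comparison.** Use the observed follow-up measurement where the graft can still be measured. Otherwise assign an unfavourable value fixed in advance, for example the worst change observed in the trial. Do not carry forward the size before failure, which would hide the harm.

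The cost is rewording in four sections, one seriousness field on the adverse event form, and possibly a few more shortened injection courses. Because the named-event stop does not depend on a serious grade, it does not by itself bring in unmasking under Protocol 3.2.3. A case that is also graded serious could.
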